2.1 Data analysis general information

All categorical data will be presented in terms of frequencies and percentages. Summaries of continuous data will be presented in terms of mean, standard deviation (SD), median, lower and upper quartiles (for most variables), minimum and maximum, the number of missing data points (for most variables) and the number of non-missing data points.

For descriptive statistics, the following number of decimal places will be used: arithmetic mean, median, lower quartile and upper quartile to 1 more decimal places than the raw data; minimum and maximum to the same number of decimal places as the raw data and SD to 2 more decimal places than the raw data. Percentages will be presented to 1 decimal place.

2.1.1 General definitions

Study treatment: Study treatment refers to:

1. Investigational treatment Treat to Target (T2T) = secukinumab 150 mg and/or 300 mg and/or adalimumab biosimilar 40 mg (GP2017)
2. Standard of Care (SOC) treatment up to the maximum recommended dose at the discretion of the investigator

The **treatment phase** is defined as the period from randomization until end of the last treatment period with treatment periods defined as:

- Period 1: date of randomization until day before visit Week 12
- Period 2: date of visit Week 12 until day before visit Week 24

- Period 3: date of visit Week 24 until day before visit Week 36

The following exceptions are made to these definitions:

- If visit Week 12 or 24 is missing but the next visit is documented, the visit date is interpolated in the middle between the earlier and the later visit.
- End dates of period 1, 2, 3: If no further visit was performed during the treatment phase after start of the period, the end date is set to the documented end of treatment date or to the period start date, if no treatment was applied in this period.
- End date of period 3: If the documented end of treatment date is on visit Week 36 date or later, the end date of period 3 is set to the end of treatment date.
- Treat-to-Target group: If treatment was not applied at visit Week 12 or 24, or the last dose of the previous period was still applied on the date of visit, the start date of period 2 resp. 3 is set to the date of first dose in this period. Cases where the last dose of the previous period was still applied on the visit date are identified by the same dose as in the previous period applied on the visit date, but treatment was switched at the first dose after the visit.

Treat-to-Target regimen

Starting from Baseline, subject will be treated with secukinumab 150 mg subcutaneous (s.c.) weekly until Week 4 and then at Week 8.

At Week 12

- If the subject achieves and maintains an ASDAS clinically important improvement (i.e. change from Baseline in ASDAS ≥ 1.1 indicating subjects is a responder), then the subject will continue with secukinumab 150 mg s.c. every 4 weeks up to Week 32.
- If the subject did not achieve ASDAS clinically important improvement (i.e. non-responder) then the subject will receive an escalated dose of secukinumab 300 mg s.c. every 4 weeks until Week 20.

At Week 24

Subjects who are receiving secukinumab 300 mg and

- Achieves ASDAS clinically important improvement (i.e. responder) will continue with secukinumab 300 mg s.c. every 4 weeks up to Week 32.
- Do not achieve ASDAS clinically important improvement (i.e. non-responder), will be switched to adalimumab biosimilar (GP2017) 40 mg s.c. every 2 weeks until Week 34.

Escape arm

- Subjects who are receiving 150 mg secukinumab (i.e. were responders at Week 12) can be escalated at Week 24 to 300 mg secukinumab every 4 weeks until Week 32 if they experience a loss of response, where loss of response is defined as ASDAS change from Baseline <1.1 .

If the ASDAS measurement is missing at a visit, it is assumed that the planned dose continues for the next treatment period.

Standard of Care Regimen

Patients will receive treatment according to local practice standards by their treating physician following the current treatment recommendations with NSAIDs as the first-choice drug treatment and disease-modifying anti-rheumatic drugs (DMARDs) for patients with active disease because of a lack of response, intolerance, or contraindication to NSAIDs ([van der Heijde et al 2017](#)). Patients will be seen every 12 weeks or more often, if clinically indicated up to Week 36; assessment of the outcome parameters will be performed at Week 12, Week 24 and Week 36.

Study treatment (T2T) start and end date: Study treatment start date is defined as the first date of study drug administration and recorded on the Drug Administration Record (DAR) Electronic Case Report Form (eCRF) page. Similarly, study drug end date is defined as the last date of study drug administration and is recorded on the DAR eCRF page.

SOC treatment start and end date: SOC treatment start date is defined as the first date of any SOC drug for AxSPA treatment after randomization. Similarly, SOC drug end date is inferred as the last date of any SOC drug administration for AxSPA treatment within the treatment phase.

Study day: Study Day 1 is defined as the first day of administration of randomized study treatment. Study day will be calculated as (event date – study drug start date + 1 day) for events that occurred on or after study drug start date (e.g. visit, lab samples, AEs). For events prior to study drug start date (e.g. time since diagnosis), study day will be negative and calculated as (event date – study drug start date).

Baseline and post-Baseline: Baseline value refers to the value of the last non-missing measurement collected prior to administration of the first dose of study treatment (screening or Baseline visit). A post-Baseline value refers to a measurement taken after the first dose of study treatment.

Change from Baseline: The difference of measure between post-Baseline and Baseline is called change from Baseline.

Percent change from Baseline: The percent change from Baseline will be calculated as below:
 $((\text{post-Baseline value} - \text{Baseline value}) / \text{Baseline value}) * 100$.

On-treatment period: The on-treatment period lasts from the date of first administration of study treatment to 30 days after the date of the last actual administration of any study treatment or end of treatment phase, whichever is later.

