¹⁰ This will be recorded in the CRF for patients in T2T arm only; in case an objective estimation of ASDAS is not possible due to e.g. an increase of CRP caused by reasons other than axSpA-related inflammation (e.g. common cold), the escalation/switch of the T2T-treatment must be done at the discretion of the investigator, the re-estimation of the ASDAS must be performed at the unscheduled visit 2 weeks later.

¹¹ Adalimumab biosimilar (Hyrimoz®) only.

Table 8-2 Drug administration schedule for treat-to-target group

Visit Week	Base line W0	Visit 1 W1	Visit 2 W2	Visit 3 W3	Visit 4 W4	Visit 5 W8	Visit 6 W12	Visit 7 W16	Visit 8 W20	Visit 9 W24	Visit 10 W26	Visit 11 W28	Visit 12 W30	Visit 13 W32	Visit 14 W34
All patients*	S150	S150	S150	S150	S150	S150									
Responder at Week 12							S150	S150	S150	S150	n/a	S150	n/a	S150	n/a
Non-responder at Week 12**							S300	S300	S300						
Escape Treatment***										S300	n/a	S300	n/a	S300	n/a
Responder at Week 24										S300	n/a	S300	n/a	S300	n/a
Non-responder at Week 24										A40	A40	A40	A40	A40	A40

Visits highlighted in grey are home administration visits, which can also be performed optionally at the study site.

A40 = adalimumab biosimilar (Hyrimoz®) 40 mg s.c.; S150 = secukinumab 150 mg s.c.; S300 = secukinumab 300 mg s.c.; W = week, n/a = not applicable

* After evaluation of response at Week 12, the patient will either continue to be treated with secukinumab 150 mg until the end of study (see row responder at Week 12) or be escalated to secukinumab 300 mg s.c.; the response will be re-assessed at Week 24 prior to study drug administration (see row non-responder at Week 12).

** After evaluation of response at Week 24, the patient will either continue to be treated with secukinumab 300 mg until the end of study (see row responder at Week 24) or switched to adalimumab biosimilar (Hyrimoz®) 40 mg s.c. (see row non-responder at Week 24).

*** In case a Week 12 responder loses his/her response at Week 24, he/she should be treated with 300 mg secukinumab at Week 24, Week 28 and Week 32.

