2.4 Treatments (study treatment, rescue medication, concomitant therapies)

2.4.1 Study treatment

Duration of exposure

The number of injections will be summarized by treatment groups, overall and within treatment periods. Duration of exposure to the study treatment will be calculated as the number of days between the first dose date and the last dose date exposed to that treatment over the specified period (expressed as: Duration of exposure = Date of last known dose of study drug – Date of first dose of study drug + 1).

The duration of exposure (in days) to the study treatment by treatment group (T2T, SOC, Other and Overall) will be summarized for the safety set as below

- a continuous variable with the standard descriptive statistics, and
- a categorical variable classified into < 12 weeks, ≥ 12 and < 24 weeks, ≥ 24 and < 36 weeks, ≥ 36 weeks with number and percentage of subjects in each category.
- On-treatment exposure = Date of last known dose of study drug – Date of first dose of study drug + 1 + 30).

Furthermore, the T2T arm will be summarized by treatment (secukinumab 150 mg, secukinumab 300 mg, adalimumab 40 mg). The T2T arm will also be summarized for actual treatment arm.

Similarly, in the SOC arm all medications will be summarized along with their drug class.

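### After a late T2T dose switch or an omitted visit dose, SAP 2.1.1 resets the start of Period 2 or 3 but not the end of the preceding period, so days and sometimes an injection fall in no period

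*SAP*

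**What the plan says.** SAP section 2.1.1 divides the treatment phase into periods by visit date: "Period 1: date of randomization until day before visit Week 12" and "Period 2: date of visit Week 12 until day before visit Week 24". Period 3 runs from the Week 24 visit to the day before the Week 36 visit.

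A list of exceptions follows. The one specific to the T2T arm opens "If treatment was not applied at visit Week 12 or 24, or the last dose of the previous period was still applied on the date" (meaning the visit date), and its consequence is that "the start date of period 2 resp. 3 is set to the date of first dose in this period". The bullet adds how to recognise such patients: the visit-date dose equals the dose of the period before, and the change comes at the first dose afterwards.

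Only one exception can move the end of Period 1 or 2 relative to the next visit, and it has its own condition: "If no further visit was performed during the treatment phase after start of the period, the end date is set to the documented end of" (here the sentence names the date on which treatment stopped, or the period start if nothing was given in that period).

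The periods are used in SAP section 2.4.1: "The number of injections will be summarized by treatment groups, overall and within treatment periods". The same section calculates exposure from first to last dose within whatever period is specified.

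**The concern.** The T2T exception changes one side of a boundary and leaves the other where it was. The periods should be contiguous, so a start that moves forward needs the preceding end to move with it. As written, the two sides separate, and whatever lies between them belongs to no period.

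The bullet also disagrees with itself. It describes the visit-date injection as the last dose of the preceding period, yet by the stated dates that period closed the day before. One programmer could follow the description and another the dates, and their injection counts would differ.

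At stake is whether the by-period injection and exposure figures are right and reconcile with the overall count. The SAP includes a way to identify these patients, so its authors expected such cases.

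**Working it through.** **Inputs.**
- Period boundaries and exceptions: SAP 2.1.1.
- Scheduled days 85, 169 and 253 for Weeks 12, 24 and 36: SAP Table 2-1. The formula day = 7 × week + 1 reproduces all three.
- T2T dosing weeks: protocol Table 8-2.
- Tolerances: protocol 6.6.1 allows ±7 days for Visits 6 to 9 (Weeks 12 to 24) and, from Visit 10 (Week 26), ±7 days on secukinumab and ±3 days on adalimumab.
- Assumption: randomization and first dose are on the same day (Day 1).

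**Does any other exception close the gap?** No. The interpolation rule for a missing visit sets the visit date itself, so it moves both sides of the boundary together. The end-date rule applies only when no further visit took place. The Period 3 end-date rule does not concern Periods 1 and 2.

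**Gap length.** The preceding period ends at visit − 1 and the next starts at the first switched dose, so gap = day of first switched dose − day of visit.
- Week 12, 150 mg to 300 mg first given at Week 16: 113 − 85 = 28 days (Days 85 to 112). With tolerances: (113 − 7) − (85 + 7) = 14 to (113 + 7) − (85 − 7) = 42.
- Week 24 escape, 150 mg to 300 mg first given at Week 28: 197 − 169 = 28 days, range 14 to 42.
- Week 24, 300 mg to adalimumab first given at Week 26: 183 − 169 = 14 days, range (183 − 3) − (169 + 7) = 4 to (183 + 3) − (169 − 7) = 24.

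**Worked case: late switch at Week 12 only, nominal schedule to Day 252.** Doses at Weeks 0, 1, 2, 3, 4, 8 and 12 (150 mg), then Weeks 16, 20, 24, 28 and 32 (300 mg): 12 injections.

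| | Period 1 | Period 2 | Period 3 | No period |
|---|---|---|---|---|
| Stated dates: days | 84 | 56 | 84 | 28 |
| Stated dates: injections | 6 | 2 | 3 | 1 |
| Preceding end moved: days | 112 | 56 | 84 | 0 |
| Preceding end moved: injections | 7 | 2 | 3 | 0 |

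By the stated dates, 224 of 252 days and 11 of 12 injections are placed. Before Week 24 the count is 6 + 2 = 8 of 9.

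**Period 1 exposure** (last dose − first dose + 1). By the stated dates the last Period 1 dose is Week 8, Day 57: 57 − 1 + 1 = 57 days. Counting the Week 12 dose: 85 − 1 + 1 = 85 days.

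**No dose at the visit.** If the Week 12 dose is omitted and 300 mg starts at Week 16, Days 85 to 112 are still unassigned, but all 6 + 2 = 8 injections given before Week 24 are placed.

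**Both switches late** (300 mg first at Week 16, adalimumab first at Week 26): 28 + 14 = 42 days and 2 of 15 injections are in no period.

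**The case against.** The strongest reply is that the intent is plain. The bullet attributes the visit-date injection to the preceding period, so a sensible programmer would count it there and no injection would be lost. The SAP introduction also defers detail to programming specifications that are not available here. This reply stands as to intent: it looks like an end date that was not updated, and nothing supports reading it as a decision to leave the dose out. It does not remove the defect, because the stated dates contradict the label and the same list writes end-date exceptions explicitly where they are wanted.

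A reader might infer two stronger claims. The documents support neither.

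- **That time at risk is lost from the safety analysis.** Adverse event tables are counts and percentages within the on-treatment period, which runs unbroken from first dose to 30 days after the last dose, or the end of the treatment phase if later. Overall exposure is last dose minus first dose plus one, not a sum of periods. That formula also omits the days between one period's last dose and the next period's first dose for patients who switch on time (nominally Days 58 to 84). Even after the correction, Days 86 to 112 stay outside within-period exposure.

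- **That patients escalated without an ASDAS are tabulated under the wrong dose.** The SAP does say "If the ASDAS measurement is missing at a visit, it is assumed that the planned dose continues for the next treatment period". That sentence closes the description of the T2T regimen, is not among the period exceptions, and does not say that it overrides recorded doses. Sections 2.2 and 2.8 analyse safety by treatment received, and 2.4.1 works from dose dates and adds a summary by actual treatment arm. Protocol Table 8-1, footnote 10, does provide that "the escalation/switch of the T2T-treatment must be done at the discretion of the investigator", but its example is an ASDAS distorted by a CRP raised for another reason. That score can be calculated, so the missing-ASDAS sentence is not triggered. What remains is that precedence between the assumption and the record is not spelled out.

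**Conclusion.** The inconsistency is real and narrow. Read by its dates, SAP 2.1.1 leaves 28 days on the nominal 4-weekly schedule (14 to 42 within tolerance) in no period for each late secukinumab dose switch, or 14 days (4 to 24) for a switch to adalimumab first given at Week 26. One injection goes with it when the old dose was given at the visit. Read by its label for that injection, nothing is lost. The text does not say which reading governs.

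The effect is confined to descriptive by-period injection and exposure figures. It would reach the adverse event split by 150 mg, 300 mg and adalimumab in section 2.8.1 only if that split uses the periods, which the SAP does not state. The Week 24 ASAS40 analysis, overall exposure and the on-treatment window do not change. The documents do not give the number of patients affected, so the effect on any table total cannot be sized.

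**What to change.** Add one sentence to the T2T exception in SAP 2.1.1: when the start of Period 2 or 3 is reset, the preceding period ends on the day before the reset start. In the worked case this places 252 of 252 days and 12 of 12 injections, and Period 1 exposure becomes 85 days. The cost is one sentence and a small programming change, with no new data and no change to treatment.

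Optionally, state in sections 2.4.1 and 2.8.1 that the dose on the Drug Administration Record defines treatment received in by-drug summaries, and whether the adverse event split by drug uses the periods.

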1.1 Study design

This is a randomized, parallel-group, open-label, multicenter study in subjects with active axial spondyloarthritis (axSpA). The aim of the study is to demonstrate that the efficacy of a Treat-to-Target (T2T) approach (with secukinumab as a first-line biologic) is superior to a Standard-of-Care (SOC) approach in terms of achieving strong clinical efficacy in patients with active axSpA who are naïve to biological therapy and who have an inadequate response to prior non-steroidal anti-inflammatory drug (NSAID) treatment. The study will include an 8-week screening period, a 36-week treatment period, and a 20-week safety follow-up period. Neither investigators nor subjects will be blinded. The primary endpoint is the percentage of subjects achieving an Ankylosing SpondyloArthritis International Society (ASAS) 40% response (ASAS40) at Week 24. At Baseline, subjects will be randomized equally to one of 2 treatment groups (T2T or SOC); a total of 300 subjects (150 subjects in each arm) will be randomized as shown in [Figure 1-1](#).

Figure 1-1 Study design

[figure not shown]
Subjects will be evaluated every 12 weeks from Baseline up to Week 36. Safety evaluations will be included in the regular visits; in addition, a safety follow-up visit will be performed 20 weeks after the last study visit (i.e. Week 36) and will take place at Week 56 for subjects completing the study according to the protocol. In addition, subjects in the T2T arm will be seen for safety monitoring at Visit 4 (Week 4) and Visit 5 (Week 8). Subjects who prematurely discontinue completely from the study for any reason should return for the final visit to conduct the Week 36 assessments (4 weeks after the last study treatment administration), then also return after an additional 20 weeks for a final follow-up visit, corresponding to Week 56 assessments.

[figure not shown]

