2.1.2 Visit windows for data analysis

Visit windows will be used for data analyses which are summarized by visit. This is based on scheduled visits and comprises a set of days around the nominal visit day. Randomization of subjects will take place at Baseline; subjects will have a maximum of 14 scheduled post-Baseline assessments and 1 follow-up assessment after 20 weeks. The data will be analyzed at Baseline, Week 12, Week 24 and Week 36. A follow-up visit will take place at Week 56.

In case of more than one post-Baseline assessment due to unscheduled visits, the assessment closest to the scheduled post-Baseline day will be used for analysis. For the summary of notable

laboratory abnormalities, the most extreme post-Baseline measurement will be used for analysis in case of more than one post-Baseline assessment. In the event two measurements are taken equally apart (e.g., 1 day before target date and 1 day after), the earlier one will be used.

Table 2-1 Assessment windows for scheduled visits

Analysis Visit	Week	Scheduled Day	Visit Window
Baseline	BSL	1	-28 days to Day 1*
Week 12	12	85	Day 2-Day 127
Week 24	24	169	Day 128-Day 211
Week 36	36	253	Day 212-Day 364

* Baseline measurement before the first drug administration.

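### SAP 2.1.1 dates Study Day, Baseline and post-Baseline from first drug, and Table 2-1 names no day count, so a late first SOC drug could put the wrong visit, or none, in the Week 24 window

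*SAP*

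**What the plan says.** **First-drug anchor (SAP 2.1.1).** Study treatment covers both arms; its second item is "Standard of Care (SOC) treatment up to the maximum recommended dose at the discretion of the investigator". The day count is set by "Study Day 1 is defined as the first day of administration of randomized study treatment", and its formula applies "for events that occurred on or after study drug start date (e.g. visit, lab samples, AEs". For SOC, "SOC treatment start date is defined as the first date of any SOC drug for AxSPA treatment after randomization". Baseline is "the last non-missing measurement collected prior to administration of the first dose of study treatment (screening or Baseline visit", and a post-Baseline value is one taken after the first dose of study treatment.

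**Randomization anchor.** The same section starts Period 1 of the treatment phase at randomization: "date of randomization until day before visit Week 12". The visit schedule in SAP 1.1 also runs from Baseline: "Subjects will be evaluated every 12 weeks from Baseline up to Week 36".

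**Windows (SAP 2.1.2, Table 2-1).** Analysis visits are assigned by Day, and the Week 24 window is "Day 128-Day 211". The text above the table refers to scheduled visits and nominal days and places randomization at Baseline, which is scheduled Day 1. The footnote ties the Baseline measurement to the first drug administration. Neither says whether Day means Study Day.

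**Consequence of an empty window.** Under SAP 2.5.3, a patient without a valid Week 24 ASAS40 assessment is a non-responder. Under SAP 2.2, everyone assigned a treatment by randomization is in the FAS.

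**The concern.** T2T patients are dosed from the Baseline visit (Protocol 6.1.2), so for them the two anchors coincide. For SOC patients nothing in the SAP makes them coincide, because the start date is whenever the first axSpA drug after randomization is recorded. Protocol 6.1 lets SOC treatment be initiated, adjusted or switched at the Week 12 visit, the Week 24 visit or unscheduled visits.

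If Table 2-1 is applied on Study Day, a late SOC start moves that patient's visits to earlier windows. The visit that supplies the primary ASAS40 value could then be the wrong one or missing, essentially in one arm of an open-label comparison. Timing adds to this. The primary analysis runs once all patients have completed Week 24 (SAP 2.5.2), so a patient whose Week 36 visit would fill the Week 24 window may not yet have had it.

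The post-Baseline definition is a separate problem. It depends on the first dose of study treatment, however Table 2-1 is read.

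**Working it through.** **Inputs.** Table 2-1 gives scheduled Days 85, 169 and 253 and windows Day 2 to 127 (Week 12), 128 to 211 (Week 24) and 212 to 364 (Week 36). The Study Day formula and SOC start date come from SAP 2.1.1. On-schedule visits are assumed.

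**Reproducing the table.** Scheduled day = 7 × week + 1, which gives 85, 169 and 253. The midpoints (85 + 169)/2 = 127 and (169 + 253)/2 = 211 are the inner window limits. So the windows are consistent with visits counted from a Day 1 at Baseline.

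**Shift under Study Day.** Let v be the visit day counted from randomization as Day 1, and k the days from randomization to the first recorded SOC drug. On or after the drug start, Study Day = v − k. Before it, Study Day = v − k − 1, because the SAP's formula then omits the added day.

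| k | Real Week 12 visit | Real Week 24 visit | Real Week 36 visit |
|---|---|---|---|
| 0 | Day 85, Week 12 | Day 169, Week 24 | Day 253, Week 36 |
| 41 | Day 44, Week 12 | Day 128, Week 24 | Day 212, Week 36 |
| 42 | Day 43, Week 12 | Day 127, Week 12 | Day 211, Week 24 |
| 84 | Day 1, no post-Baseline window | Day 85, Week 12 | Day 169, Week 24 |
| 125 | Day −41, none | Day 44, Week 12 | Day 128, Week 24 |
| 126 | Day −42, none | Day 43, Week 12 | Day 127, Week 12 |

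- The Week 36 visit is in the Week 24 window when 128 ≤ 253 − k ≤ 211, that is, for k = 42 to 125. Over that range the real Week 24 visit is on Day 169 − k, from 127 down to 44, inside the Week 12 window.
- At k = 84 (first SOC drug at the Week 12 visit), the Week 24 and Week 36 visits fall exactly on the Week 12 and Week 24 target days.
- From k = 126, 253 − k is at most 127, so no Week 12, 24 or 36 visit is in the Week 24 window. Without an unscheduled assessment there, SAP 2.5.3 imputes non-response.
- If the Week 36 visit is 7 days early, 246 − k must lie in 128 to 211, giving k = 35 to 118. If it is 7 days late, 260 − k gives k = 49 to 132. The 7 days are an assumption for SOC, because Protocol 6.6.1 states visit tolerances for T2T only.

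**Post-Baseline, independent of Table 2-1.** Protocol 8.3 places efficacy assessments before administration of study or reference treatment. With a first SOC drug at or after the on-schedule Week 12 visit (k ≥ 84), the Week 12 values precede the first dose and so are not post-Baseline under SAP 2.1.1. The same holds for the Week 24 values at k ≥ 168.

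**No SOC drug.** Such a patient has no Study Day but remains in the FAS.

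**With randomization as Day 1.** k drops out, and on-schedule visits fall on Days 85, 169 and 253, each in its own window.

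**The case against.** The strongest reply is that Table 2-1 never says Study Day. SAP 2.1.2 speaks of scheduled visits around a nominal day and puts randomization at Baseline, scheduled Day 1. On that reading the table already counts from randomization and its windows are right. This stands as a fair reading. It is not stated, though, and choosing the assessment closest to the scheduled day needs some day count.

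Second, the Study Day formula uses the study drug start date, which SAP 2.1.1 ties to the drug administration record under the T2T heading; the SOC date has its own name. Applying the formula to SOC is therefore an inference from the definition of study treatment. If the inference is refused, SOC patients have no Study Day at all, which also needs repair.

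Third, long delays should be uncommon. Protocol 6.3.1 and 6.7.2 expect SOC treatment from the randomization/Baseline visit, Protocol 8.1.1 treats failure to start as early termination, and a continued NSAID, methotrexate or sulfasalazine may set a start date near randomization. This stands and limits the size of the point. The SAP does not say, however, whether a continued drug sets the SOC start date, whereas SAP 2.4.2 covers continued drugs explicitly for concomitant medication.

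Finally, SAP section 1 refers to separate programming specifications, which may already settle the visit derivation. They are not available here, and the anchor for a primary-endpoint window belongs in the SAP.

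**Conclusion.** The concern holds in conditional form. SAP 2.1.1 uses a first-drug anchor for Study Day, Baseline and post-Baseline alongside a randomization anchor for treatment periods, and Table 2-1 does not say which its Days follow. If they are Study Days and visits are on schedule, a first recorded SOC drug 42 to 125 days after randomization puts the Week 36 visit in the Week 24 window; from 126 days the window holds no Week 12, 24 or 36 visit. The post-Baseline definition and the undefined Study Day for an untreated SOC patient need repair on either reading of the table.

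A reader might infer that the SAP definitely scores the wrong visit in the SOC arm. The documents do not support that, because counting Table 2-1 from randomization is also open. A reader might also infer a bias towards T2T or a loss of power. Neither can be stated: the number of SOC patients starting this late is not given, and the effect on a patient's response status could go either way, since a Week 36 value may be better or worse than the Week 24 value it replaces.

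**What to change.** In SAP 2.1.1 and 2.1.2, state for efficacy in both arms that:

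- Table 2-1 days are counted from the date of randomization as Day 1.
- Baseline is the last non-missing value on or before randomization and before any T2T dose.
- Post-Baseline means after that point.

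Keep first-drug dates for exposure and safety only, and say whether a drug continued from before randomization sets the SOC start date. Optionally, report how many SOC patients have a first SOC drug 42 or more days after randomization, 126 or more days after it, or none.

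The cost is a few sentences and one derivation in the programming specification. No new data are needed.
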